3.2.2 Screening Failures

All subjects signing consent who do not have at least one vessel transection attempted by ENSEAL X1 during their procedures will be recorded as screen failures. For subjects who are determined to be screen failures, only the relevant electronic eCRF pages (inclusion/exclusion criteria, demographics, AEs, subject completion/discontinuation) will be completed.

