3.0 INVESTIGATIONAL PLAN

3.1 OVERALL STUDY DESIGN AND PLAN - DESCRIPTION

This prospective, single-arm, multi-center study will collect clinical data in a post-market setting by procedure group (upper GI, lower GI, and gynecological). Investigators will perform each procedure using the device in compliance with their standard surgical approach and the ENSEAL X1 and GEN11 IFUs.

Subjects will be consented and screened anytime during a period of 8 weeks prior to the date of surgery. Subjects will be considered enrolled when the ENSEAL X1 device has been attempted to be used for a vessel transection during upper GI, lower GI, and gynecological procedures. All subjects enrolled will be followed post-operatively through discharge and again at 28 days (± 14 days) post-surgery; therefore, from the surgery date to study exit, the duration will be approximately 6 weeks.

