 11 NOV 2022

utilizing consecutive screening and enrollment in an effort to generate a random and representative patient population sample. All eligible subjects (Sections 3.2.3 and 3.2.4) will be considered enrolled at the time when the ENSEAL X1 device has been attempted to be used for a vessel transection during one of the proposed procedure groups. Up to 16 surgery centers (United States and/or European Union and/or United Kingdom) will be selected as study sites. Each participating investigator is expected to perform a minimum of two procedures using the ENSEAL X1 device. A minimum of 133 subjects (maximum of 149 subjects) will be included in the study to achieve a total of 230 vessel transections. The enrollment is planned with the following procedure targets:

- A minimum of 77 subjects enrolled to a maximum of 89 subjects enrolled for upper GI procedures which will contain the following subgroups with corresponding enrollment restrictions:
 - A minimum of 14 subjects enrolled to a maximum of 17 subjects enrolled for fundoplication (Nissen, anterior or posterior [Toupet]) or hiatal hernia procedures);
 - A minimum of 27 subjects enrolled to a maximum of 30 subjects enrolled for gall bladder procedures;
 - A minimum of 10 subjects enrolled to a maximum of 13 subjects enrolled for sleeve gastrectomy procedures;
 - A minimum of 26 subjects enrolled to a maximum of 29 subjects enrolled for small intestine resection procedures (also includes RYGB and BPD/DS),
- A minimum of 28 subjects enrolled to a maximum of 30 subjects enrolled for lower
 GI procedures (e.g., large intestine resections); and
- A minimum of 28 subjects enrolled to a maximum of 30 subjects enrolled for gynecological procedures (hysterectomies associated with oophorectomies). The planned use of the ENSEAL X1 device should be for both the hysterectomy and oophorectomy steps of the procedures.

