5.6 ANALYSIS SETS

The summary of all performance and safety endpoints will be performed on the set of subjects in whom the ENSEAL X1 device is utilized during the surgical procedure. The summary of all performance and safety endpoints will be performed by procedure group and procedure subgroup on the entire pooled set of subjects. The hypotheses described in Section 5.4 will be evaluated on the pooled set of subjects as data on the ENSEAL X1 Large Jaw device demonstrated consistent performance across procedure groups in a similar study (>94% Grade 3 or lower hemostasis achieved for each procedure group).

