As this is a single-arm study, no randomization will occur, and no blinding procedures are required.

4 Interval Windows

Interval windows for the purpose of analysis in this study will not be defined outside of those already specified in the protocol for visit scheduling as the collection of data for the primary and secondary performance endpoints occurs intra-operatively. The final visit occurs approximately 4 weeks after surgery, thus no interval windows need to be defined given the absence of long-term follow-up in this study. The Schedule of Events specifies a window of 14 days around the scheduling of the 4-week follow-up visit, and any information entered in the eCRFs at this visit will correspond to the 4-week visit. There will be no assigning of observations to time points outside of the visit to which they are recorded in the eCRFs.

5 Levels of Significance

The statistical hypothesis for the primary endpoint will be evaluated using a one-sided significance level of 0.025. A 95% confidence interval will be provided for the primary endpoint. Estimation of primary endpoint by procedure group and procedure subgroup will provide 95% confidence interval. Estimation of secondary and safety endpoints will be summarized by number and percentages only.

6 Analysis Sets

Full Analysis Set: Full Analysis Set (FAS) will include subjects for whom the ENSEAL X1 device is utilized during the surgical procedure and have assessment for the primary endpoint. The FAS includes subjects for whom the answer is "Yes" to at least one of the following questions from the "ENSEAL X1 Usage" form on eCRF: "Were adhesions removed or divided by ENSEAL X1", "Were lymphatics bundles divided by ENSEAL X1", "Were tissue bundles divided by ENSEAL X1", "Was the ENSEAL X1 used for tissue grasping", "Was the ENSEAL X1 used for tissue dissection." The summary of all primary and secondary performance endpoints will be performed using FAS by procedure group (upper GI, lower GI, and gynecological), procedure subgroup (fundoplication, gall bladder, sleeve gastrectomy, and small intestine resection) and on the entire pooled set of subjects.

Safety Analysis Set: The Safety Analysis Set (SAS) will include all subjects who signed informed consent and for whom the ENSEAL X1 device is utilized during the surgical procedure. The safety endpoints will be summarized using SAS by procedure group, procedure subgroup and in total.

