8.7 Handling of Missing Data

All summaries will be performed for enrolled subjects only and with observed data. There will be no imputation of data for early terminated subjects or for missing data within the database.

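### Subjects exposed to ENSEAL X1 without any attempted vessel transection belong in the safety set by definition, but as screen failures they have no usage form and no specified Day 28 visit

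*Protocol*

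**What the plan says.** **Enrollment and screen failure.** Protocol 3.2.1 says eligible subjects "will be considered enrolled at the time when the ENSEAL X1 device has been attempted to be used for a vessel transection". Protocol 3.2.2 says consented subjects "who do not have at least one vessel transection attempted by ENSEAL X1 during their procedures will be recorded as screen failures". Other use of the device makes no difference to this status. For screen failures, "only the relevant electronic eCRF pages (inclusion/exclusion criteria, demographics, AEs, subject completion/discontinuation) will be completed".

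**Follow-up.** Protocol 3.1 states: "All subjects enrolled will be followed post-operatively through discharge and again at 28 days". The synopsis and SAP 1.2 say the same. No follow-up is stated for screen failures.

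**Safety population.** Protocol 5.6 says the summaries of performance and safety endpoints "will be performed on the set of subjects in whom the ENSEAL X1 device is utilized during the surgical procedure". In SAP Section 6 the Safety Analysis Set "will include all subjects who signed informed consent and for whom the ENSEAL X1 device is utilized during the surgical procedure". Neither definition requires an attempted transection.

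**Restriction on summaries.** SAP 8.7 states: "All summaries will be performed for enrolled subjects only and with observed data". SAP 1.2 ties enrollment to an attempted transection. SAP Section 6, however, defines an All Enrolled Set of everyone who consents, and SAP 8.2 tabulates screen failures within it.

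**Non-transection use.** Adhesiolysis, division of lymphatics or tissue bundles, grasping, cutting and dissection are rated as a secondary endpoint (Protocol 2.2). SAP Section 6 names the ENSEAL X1 Usage form as the place where such use is recorded.

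**The concern.** The plan declares one safety population and collects data for a different one. Exposure to the device defines the safety set. An attempted transection decides who gets the usage and surgical pages and the Day 28 visit. A subject can meet the first condition and fail the second.

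The step from one to the other comes after exposure and can be caused by the device. An injury or malfunction during dissection may lead the surgeon to put the device aside before any vessel is reached, and that subject is then a screen failure. SAP 8.5.1 names thermal damage or injury as a key safety outcome. If it first shows itself after discharge, no scheduled contact is specified that would find it. The safety endpoint is a count of device-related adverse events in a sample of this size, so one event more or less is visible in the result.

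**Working it through.** **1. The subject traced through the documents.** Take a consented subject in whom ENSEAL X1 divides adhesions and no vessel transection is ever attempted.

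| Rule | Consequence for this subject |
|---|---|
| Protocol 3.2.1 | Not enrolled |
| Protocol 3.2.2 | Screen failure; eligibility, demographics, adverse event and completion pages only |
| Protocol 3.1, SAP 1.2 | Day 28 visit not specified |
| Protocol 5.6, SAP Section 6 (Safety Analysis Set) | In the safety set |
| SAP Section 6 (All Enrolled Set) | In disposition and all listings |
| SAP 8.7, enrolled as in SAP 1.2 | Left out of all summaries |
| SAP 8.7, enrolled as in the All Enrolled Set | Kept in the summaries |

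**2. Can safety-set membership be derived?** If a device-related event is reported, yes, indirectly: the adverse event record includes the relationship to the study devices (Protocol 6.4.1). If none is reported, no. On the four listed pages this subject looks the same as one in whom the device was never used.

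**3. The plan's own safety figures** (Protocol 5.7, SAP Section 7; n = 133, incidence 1%).
- Probability of at least one event: 1 − 0.99^133 = 73.7%. This reproduces.
- Exact two-sided 95% upper limit for 0/133: 1 − 0.025^(1/133) = 2.74%. This agrees with the stated bound of less than 2.8%.

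**4. Illustration.** The documents give no number of exposed subjects without a transection attempt. Call it k and assume k = 1, 5 or 10. With no event the upper limit is 1 − 0.025^(1/n), where n = 133 + k. With one event it is the p that solves (1 − p)^n + n·p·(1 − p)^(n−1) = 0.025.

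| k | n | Upper limit, no event among the k | Upper limit, one event among the k |
|---|---|---|---|
| 1 | 134 | 2.72% | 4.09% |
| 5 | 138 | 2.64% | 3.97% |
| 10 | 143 | 2.55% | 3.83% |

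Adding event-free subjects hardly moves the limit. One missed event takes it above 2.8% in each case shown.

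**The case against.** A reader might infer that device injuries before the first transection drop out of the safety endpoint. The documents do not support that.

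- The adverse event page is kept for screen failures, and Protocol 6.4.1 requires attributable events to be recorded and followed to resolution or stability. Device complaints are reported separately within 24 hours, with an adverse event form if a safety event is involved (Protocol 7.1.1).
- The Safety Analysis Set wording includes these subjects. SAP 8.5 summarizes and lists all reported events.
- If a transection is attempted later in the same operation, even unsuccessfully, the subject is enrolled and earlier injuries count. Only subjects who never reach an attempt are affected.
- SAP 8.7 sits under missing data and excludes them on one reading only. Its protocol counterpart, 5.9.6, limits summaries to subjects undergoing the scheduled procedure, not to those with an attempted transection.

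Nor can a downward bias in the event rate be taken as established. Leaving out exposed, event-free subjects shrinks the denominator and pushes the rate up. Downward bias needs missed events or the restrictive reading of 8.7. The 0/133 figure is a planning illustration, there is no safety hypothesis, and SAP Section 5 limits safety results to numbers and percentages. Eligibility also requires a planned transection, so few subjects should be affected.

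All of this stands. It does not supply the usage form or the Day 28 contact, and it does not settle what SAP 8.7 means. The lack of follow-up is itself an inference: no section forbids a visit for these subjects, but none specifies one.

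**Conclusion.** The point holds as a mismatch between the declared safety set and the data collected for it. For subjects exposed without a transection attempt:

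- membership of the safety set cannot be derived unless a device-related event is reported;
- events first appearing after discharge may be missed;
- SAP 8.7 gives two opposite answers on whether they are summarized.

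The size is unknown and probably small. The move from an upper limit of 2.74% (0/133) to 4.09% (1/134) assumes no events among 133 enrolled subjects and exactly one missed event in a single exposed screen failure. It shows how sensitive a near-zero count is and does not estimate bias. The conclusion also assumes that the page list in Protocol 3.2.2 is exhaustive, as its wording indicates. The primary analysis is not affected, because its denominator is vessel transections. The change should be made, since it is cheap and brings the data into line with the plan's own definition.

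**What to change.** - **Protocol 3.2.2:** limit screen failure to consented subjects in whom ENSEAL X1 was not used on tissue.
- **Exposed without a transection attempt:** complete the ENSEAL X1 Usage, intra-operative and adverse event pages and Visit 3, which Protocol 3.6.3 already allows by telephone. State in Protocol 3.1 and SAP 1.2 that these subjects are followed, and include them in the Safety Analysis Set.
- **Enrollment and primary analysis:** state that these subjects do not count toward the enrollment targets. Leave the vessel denominator unchanged.
- **SAP 8.7:** replace the restriction to enrolled subjects with a reference to the analysis set named for each summary.

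The cost is wording in two documents and a few extra forms and calls. The reported safety rate may be slightly less favourable.

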3.2.3 Inclusion Criteria

Subjects satisfying the following criteria will be considered eligible for enrollment in this study:

- Primary laparoscopic or open procedure (upper GI, lower GI, and gynecological) where at least one vessel is planned to be transected by the ENSEAL X1 device per the IFU;
- 2. Willingness to give consent and comply with all study-related evaluations and treatment schedule; and

Study Number: ENG_2019_01 CONFIDENTIAL Page 16 of 34
Version: Amendment 5 11 NOV 2022

3. At least 18 years of age.

3.2.4 Exclusion Criteria

Subjects meeting the following criteria will be considered ineligible for enrollment in this study:

- 1. Physical or psychological condition which would impair study participation; or
- 2. Enrollment in a concurrent interventional clinical study that could impact the study endpoints.

3.2.5 Removal of Subjects from Study

A subject has the right to withdraw from the study at any time for any reason without prejudice to his/her future medical care by the physician or the institution. Should a subject (or subject's legally authorized guardian/representative) decide to withdraw, 1) all data collected up to the point of withdrawal will be considered for analysis; and 2) all efforts will be made to collect and report the final visit observations as thoroughly and timely as possible. Participation may be terminated prior to completing the study for any of the reasons listed below (reasons that do not fit the categories below will be documented as "other").

Adverse Event

When the subject experiences an AE and the Investigator or Medical Monitor believes it is in the best interest of the subject to discontinue participation in the study, the subject will be withdrawn from the study.

Lost to follow-up

When contact with the subject has been lost without completing a final contact assessment, and every attempt to contact the subject has failed, the subject will be considered lost to follow-up. All attempts to contact the subject requesting his/her return for the final visit must be documented.

Withdrawal of consent

Any method of contact with the subject (or subject's legally authorized guardian/representative) in which he/she state they no longer want to participate in the study specific activities constitutes withdrawal of consent for participation in the study. When possible, the reason for withdrawal will be documented.

Site Termination or Study Termination

A study site or the entire study may be terminated. When this occurs, all subjects currently enrolled at the site will be withdrawn and documented as early terminations. Reasons for site or study termination may include, but are not limited to the following:

- Administrative concerns (e.g., inadequate subject enrollment, Investigator/institution non-compliance, change of business strategy, etc.);
- Safety Issues, including those due to non-compliance, which substantially affect
 the risk to benefit ratio of the study subjects at a site or for the study as a whole; or
- Regulatory Body Mandate(s).

The Investigator has the right to terminate the subject's participation at any time. Should this be necessary, procedures for termination will be provided by the Sponsor.

Death

• When possible, the cause of death will be documented.

Other (which may include)

Investigator recommendation.

3.2.6 Subject Replacement in Study

Subjects who withdraw or are terminated early from the study will not be replaced.

3.3 STUDY PROCEDURES

3.3.1 Procedure Description

Elective upper GI, lower GI, and gynecological procedures where ENSEAL X1 is indicated for use will be performed per the institution's SOC. Only the principal investigator or sub-Investigator can use the device during the vessel transections. For the gynecological procedures, the planned use of the ENSEAL X1 device should be for both the hysterectomy and oophorectomy steps of the procedures.

3.3.2 Identity of Study Products

The ENSEAL X1 and the GEN11 are the study products for this study.

3.3.2.1 Device Description

ENSEAL X1

The ENSEAL X1 instrument is a sterile, single-patient-use surgical instrument to coagulate and transect vessels up to and including 7 mm in diameter, tissue and/or vascular bundles. This device is to be used for soft tissue only. The instrument consists of a grip housing assembly, a rotating shaft, a moveable jaw, and a knife. The instrument shaft can be rotated 360° to facilitate visualization and enable easy access to targeted tissue. The jaws are in a normally-opened position and can be partially or fully closed by squeezing the closing handle. The jaws are designed for grasping and holding targeted tissue when clamped. The ENSEAL X1 has separate seal and cut capabilities. The lower jaw of the ENSEAL X1 can be used in the open or closed position to deliver energy based on the electrode configuration and jaw design. Bipolar energy is delivered when the SEAL button on the device or the MIN foot pedal is pressed. Pressing the CUT button advances the knife the length of the jaws to cut the targeted tissue. The power cord is permanently attached to the device and connects the instrument to the generator. The ENSEAL X1 instrument is designed for use exclusively with the GEN11 software version 2016-1 or later, packaged separately.

GEN11

The GEN11 device supplies energy to the HARMONIC and ENSEAL surgical instruments. The generator uses a touchscreen display interface and has a unique receptacle port that accepts either a HARMONIC or an ENSEAL instrument. Connectors (HGA11 for HARMONIC and EGA11 for ENSEAL) are used to enable the generator to power legacy instruments.

3.3.2.2 Indications

ENSEAL X1

The ENSEAL X1 are bipolar electrosurgical instruments for use with an electrosurgical generator. They are intended for use during open or laparoscopic surgical procedures to cut and seal vessels, and to cut, grasp and dissect tissue during surgery.

Indications for use include open and laparoscopic general, gynecological, urologic, thoracic, and ENT surgical procedures or any procedure where vessel ligation (cutting and sealing), tissue grasping, dissection, and division of vessels, lymphatics, and tissue bundles is performed (e.g. bowel resections, hysterectomies, gall bladder procedures, Nissen Fundoplication, adhesiolysis, and oophorectomies). The devices can be used on vessels up to and including 7 mm and bundles as large as will fit in the jaws of the instruments.

The ENSEAL X1 have not been shown to be effective for tubal sterilization or tubal coagulation for sterilization procedures.

GEN11

The GEN11 provides radiofrequency power to drive ENSEAL electrosurgical instruments that are used during open or laparoscopic general and gynecological surgery to cut and seal vessels and to cut, grasp, and dissect tissues. In addition, the generator provides power to drive HARMONIC ultrasonic surgical instruments that are indicated for soft tissue incisions when bleeding control and minimal thermal injury are desired.

ENSEAL and HARMONIC instruments, when used with the GEN11, have not been shown to be effective for sterilization procedures or tubal coagulation.

3.3.2.3 Contraindications

ENSEAL X1

The efficacy of the ENSEAL X1 for the indication of contraceptive tubal coagulation (permanent female sterilization) has not been evaluated and is unknown. The design of the ENSEAL tissue sealing device is significantly different from bipolar designs that are marketed for the indication of contraceptive tubal coagulation. The design differences may affect the efficacy of the procedure and failure rates may not be comparable.

GEN11

The use of the GEN11 and the attached instruments are contraindicated when, in the judgement of the physician, radiofrequency or ultrasonic surgery would be contrary to the best interest of the patient. The instruments are not indicated for incising bone.

3.3.2.4 Labeling of Study Products

The ENSEAL X1 has received 510(k) clearance in the United States by the Food and Drug Administration (FDA) and has CE Mark in the European Union and United Kingdom. The GEN11 has clearance for distribution in the United States by the FDA and is CE marked in the European Union and United Kingdom. The study devices will use the cleared labeling. The Sponsor requires no additional labeling in this study.

3.3.2.5 Accountability of Study Products

The ENSEAL X1 may be provided to the participating institutions. The GEN11 (including footswitches) may be loaned to any institution in the study. Each institution not provided with ENSEAL X1 will use devices acquired through normal procurement process. If

institutions are provided ENSEAL X1, the devices will be tracked using shipping receipts and device accountability logs and all device returns will be managed by contacting EES. Devices provided for the study must be kept in a secure area and used only for treating subjects participating in the study, in accordance with the protocol. If applicable, the study device inventory must be available for periodic inspection/verification.

3.3.3 Prior and Concomitant Therapy

Subjects will be assessed for certain prior medication therapy used up to 30 days prior to surgery. These medications include aspirin, antiplatelet agents, nonsteroidal anti-inflammatory drugs, and anticoagulants. Review will occur during Visit 1 (Screening Visit) and Visit 2 (Procedure Visit).

Subjects will be assessed for occurrence of pre-surgical radiation/chemotherapy used up to 90 days prior to surgery. Review will occur during Visit 1 (Screening Visit) and Visit 2 (Procedure Visit).

Subjects may continue with their current medical care while in the study and the following medications will be collected for this study:

- Certain prior medication therapy used up to 30 days prior to surgery (listed above);
 and
- Any medications administered during the study due to a device-related or procedure-related AE.

